The researchers will deliver the Intervention with the patients participating in the study at leaving points, during the patient's journey through the COPD service, as specified in the diagram below. Patients enter the pulmonary rehabilitation (PR) section of the COPD service post-acute episode or by GP referral. Patients are then clinically assessed for suitability to continue in the exercise component of the service. If patients are deemed suitable for exercise then they continue onto PR. Post PR they have a review, 30 minutes with a clinician to ascertain their progress through the programme and to recommend continuation of exercise. At this point patients can also leave the programme.

Furthermore patients are offered maintenance exercise therapy – and are reviewed yearly, during these reviews other exercise and activity can also be recommended, patients can also leave the service at this point. These transition points in the care pathway; leaving the PR programme, or at

yearly maintenance review patients will be offered to participate in the GENIE study and provided with study information.

1. Those patients completing a PR programme, and in whom we wish to provide clear direction and signposting to appropriate social activity
2. Those who have benefitted from maintenance for 1 year or more, but at review could be encouraged to do more and have more social outlets.

Currently, patients leaving PR classes are usually offered the option to join the maintenance exercise class, delivered by the COPD team, other exercise options are considered, however, these options are currently limited or difficult to access in one place.

Building capacity to carry out the evaluation: Ensuring the GENIE database contains an appropriate library of social and health activities suitable for the Southampton COPD patient. The lead researcher will investigate existing exercise, social and community activities, then populate and categorise the GENIE database.

Introducing the intervention: In order to successfully implement the GENIE tool into clinical practice; the clinical team needs to be at the core of the process in order to ensure appropriate and effective facilitation. Therefore, the clinical team will be briefed as the study progresses, through question and answer sessions and direct learning opportunities in how the tool works and the objectives of the study.

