Selection and patient information: Patients in the COPD service; at the outset of their assessment, the end of PR and during maintenance sessions will be informed that the GENIE implementation evaluation is in progress.

Patients participating in these aspects of the service will be offered the opportunity to volunteer for the study, by the clinical team. If patients are interested they can then provide their names to the clinical staff to keep on a secure Solent database. Patient information sheets and invitation letters will be given out to the interested patients at their clinical visits to minimise postal and /or extra visits.

Once patients have received an information sheet, they will be allowed at least 72 hours to read and digest the information, (patient information sheets, consent and GP letters are separate documents), and share this with their friends and family if they wish to. Ideally, patients are provided with information in their clinical visits and are returning for clinical visits then appointments for research could be amalgamated with usual clinical visits. In this way extra study visits can be reduced. Patients, now participants, will be invited to consent and be randomised at the point of leaving usual clinical care. Furthermore, all patients at this point will have the opportunity to opt out of the study.

Once the participant is randomised (using block randomisation technique in clinic), then they will all receive normal clinical care (discharge planning with suggested activities), and the GENIE tool intervention, in the GENIE group, this is in addition to usual clinical care. Baseline questionnaires will also be administered at this visit.

The follow up period will commence 3 months (12 weeks) (+/- 1 week) from the day the GENIE tool was initially delivered. Participants will be invited back, via letter and /or phone call to attend their three month follow up visit at Bitterne Health Centre.

Solent NHS Trust will be the overall NHS organisation with one venue for study delivery; Bitterne Health Centre.

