Block randomisation technique, a commonly used technique in clinical trial design to reduce bias and achieve balance in the allocation of participants to treatment arms, especially in this case when the sample size is small (Efird, J. 2010). In order to reduce unconscious bias of the researcher, pre-prepared envelopes containing the possible combinations of group allocation, will be stored in a locked drawer in Bitterne Health Centre. The intention is to randomize in blocks of four, as this will complement the clinic structure. Therefore, each envelope will contain a pre-determined allocation pattern for that clinic (AABB, ABAB, BABA etc.).

The researcher team will share an excel spread sheet which will be set to generate a random number sequence. The next sequential number will be selected, which will then correspond to an envelope with the predetermined sequence. In this way the envelope selection is random, then sequence in the envelopes is also random, but ensures 50/50 grouping of participants. Baseline data for descriptive statistics will also be collected. (Data capture form appended)

In order to conduct meaningful analysis recruitment needs to reach at least 30 patients, in each group, however the maximum could be 60 in each group, 120 patients in total. Therefore recruitment could take between 6-9 months. The timeframe can be increased if necessary.

Initial / Baseline data collection:

Socio-economic data will be collected including; disease severity (FEV1), gender, EQ-5D, health care utilisation questionnaire, HEIQ and wellbeing questionnaires (CAT, GAD, PHQ-9), as well as an optional health behaviour questionnaire, from both the usual care group and the interventional group. Please note CAT, GAD, PHQ-9 FEV1 and gender are already captured routinely during clinical consultation.

Intervention

[figure not shown]
Assessment stratification and feedback:

Stage 1: The patient will complete a questionnaire online with the researcher/clinician. The patients will be asked to name the important people and activities in their network, type of relationship and frequency of contact using the concentric circles diagram.

Stage 2: The online process: consisting of series of questions will be used to elicit the participant's values and preferences for activities and support resources.

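### The researchers who deliver GENIE share the sheet that sets the envelope order, and each envelope holds four allocations, so the procedure as written does not conceal allocation

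*Combined protocol and SAP*

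**What the plan says.** All references are to the combined protocol and SAP.

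- **Source of the order** (Implementation Design, block randomisation paragraphs): "The researcher team will share an excel spread sheet which will be set to generate a random number sequence". It continues: "The next sequential number will be selected, which will then correspond to an envelope with the predetermined sequence".
- **Block size** (same paragraphs): "The intention is to randomize in blocks of four, as this will complement the clinic structure".
- **Content of an envelope** (same paragraphs): "each envelope will contain a pre-determined allocation pattern for that clinic (AABB, ABAB, BABA etc". One envelope therefore serves four patients.
- **Safeguard** (same paragraphs): "pre-prepared envelopes containing the possible combinations of group allocation, will be stored in a locked drawer in Bitterne Health Centre". The stated aim is to limit researcher bias.
- **Who delivers GENIE** (Implementation Design): "The researchers will deliver the Intervention with the patients participating in the study at leaving points". The Quality Assurance section also has the research team delivering it.
- **Timing** (Selection and patient information): "Patients, now participants, will be invited to consent and be randomised at the point of leaving usual clinical care". Patients may still opt out at that point.
- **Size**: 30 to 60 per group, at most 120 in total, split equally.

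The text does not say that the number sequence is generated once and frozen, that someone outside recruitment and delivery holds it, or that draws are logged. Nor does it say that envelopes are sealed, opaque and single-use, who holds the key to the drawer, or whether all four patients must have consented before a block envelope is opened.

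**The concern.** Concealment requires that nobody who can influence a patient's entry knows the next allocation. Here the people who deliver the intervention also share the sheet that picks the next envelope. The drawer protects unopened envelopes. It does not protect the sheet, and it does nothing once a block envelope has been opened.

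Three routes to foreknowledge or influence follow, and they differ in strength:

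1. **Whole-block disclosure.** This follows from what an envelope contains and needs no assumption about the number of envelopes. It fails only if all four patients have consented before opening.
2. **Redrawing.** This is left open because the order is not stated to be fixed.
3. **Reading the next number.** This matters only if the contents of the corresponding envelope are already known, for example because that envelope has been used before.

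Consent, the chance to opt out and randomisation all fall at the same point. Someone who knows the next allocation could affect who is booked into a slot or how firmly consent is sought. CAT, EQ-5D and healthcare use are all reported by the patient. The Analysis Plan compares the clinical outcomes between groups at 3 months by a Wilcoxon test and states no baseline adjustment, so imbalance from selective entry would pass into the result.

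**Working it through.** **Inputs.** Block size 4, equal allocation, and 30 to 60 per group, all from the block randomisation paragraphs. The number of envelopes is not given and is varied below.

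**Step 1: the plan's own figures.** 2 × 60 = 120 patients, and 120/4 = 30 full blocks. At the minimum, 2 × 30 = 60 patients, and 60/4 = 15 full blocks. The plan's totals are consistent with blocks of four.

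**Step 2: number of patterns.** Two A and two B in four places: 4!/(2! × 2!) = 6, namely AABB, ABAB, ABBA, BAAB, BABA, BBAA.

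**Step 3: disclosure within a block, with no re-use assumed.**

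- Block envelope opened at the first patient: the other 3 of 4 allocations are known, 3/4 = 75%. That is 45 of 60 or 90 of 120 patients. With an even guess for the first patient, the share guessed correctly is (0.5 + 3)/4 = 87.5%.
- Comparison, one concealed allocation per envelope, with block size 4 known and earlier allocations seen: the chances of a correct guess at places 1 to 4 are 1/2, 2/3, 2/3 and 1, so the mean is 2.833/4 = 70.8%. The chances that a place is fully determined are 0, 0, 1/3 and 1, so the mean is 1.333/4 = 33.3%.
- Block envelope opened only after all four have consented: no allocation is disclosed before consent.

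**Step 4: re-use of envelopes (assumption).** For B blocks drawn at random with replacement from k envelopes, the expected number of blocks that use an already opened envelope is B − k(1 − (1 − 1/k)^B).

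| Assumption | 15 blocks (60 patients) | 30 blocks (120 patients) |
|---|---|---|
| One envelope per pattern, k = 6 | 15 − 6(1 − (5/6)^15) = 9.4, or 63% | 30 − 6(1 − (5/6)^30) = 24.0, or 80% |
| k = 15, with replacement | 36% | not calculated (fewer envelopes than blocks) |
| k = 30, with replacement | 20% | 36% |
| k = 60, with replacement | 11% | 21% |
| Single-use envelopes | 0% | 0% |

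With six envelopes, re-use is forced in at least 15 − 6 = 9 or 30 − 6 = 24 blocks. The expected numbers correspond to about 38 of 60 or 96 of 120 patients. In a re-used block, the next number on the sheet discloses all four allocations.

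**Step 5: redrawing (assumption).** If the sheet can be recalculated and the envelope contents are known, the chance that the first place in a block is a wanted arm is 1 − 0.5^(r+1) with r redraws allowed. This gives 50%, 75%, 87.5% and 93.8% for r = 0, 1, 2 and 3.

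Steps 3 to 5 measure predictability. None of them measures the resulting bias in CAT, EQ-5D or healthcare use.

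**The case against.** The strongest reply is that much of this is inference.

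- **Re-use is not stated.** A reader might infer six re-used envelopes from "pre-prepared envelopes containing the possible combinations of group allocation". Those words describe what the envelopes contain and not how many there are. The later reference to a pattern for that clinic can equally mean a fresh envelope for each session. This stands: the 63% and 80% are conditional figures.
- **Redrawing is not stated, and it pulls against visibility.** If the sheet recalculates, the numbers shown ahead are a poor forecast. If the list is stable, it cannot simply be regenerated. This stands against asserting both faults together. The text leaves open which applies and rules out neither.
- **A visible number is not a visible arm.** It discloses an allocation only to someone who knows that envelope's contents. This stands.
- **Researchers do not make the first approach.** A reader might infer that they know a block before anyone is approached. The documents do not support that. Selection and patient information has the clinical team offer the study and allows at least 72 hours to read the information, and Population says every patient in the programmes will be offered participation. What remains is possible influence on booking and consent, because the text does not say who controls them.
- **A clinic of four might all consent first.** Tying blocks to the clinic makes this possible, and it would close the within-block disclosure. The text does not require it.
- **The enrolment and randomisation figure is not available here** and may add detail. The point is therefore about what the text states.

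None of this removes the core: the delivering team shares the ordering sheet, and one opening exposes four allocations.

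**Conclusion.** The concern holds in a limited form. As written, the procedure does not conceal allocation. The team that delivers GENIE shares the sheet that orders the envelopes, and opening one envelope for its first patient discloses 75% of that block before the other three patients are allocated. This rests on one condition, that the four have not all consented beforehand, and the text does not require that they have.

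Two additions are conditional. Redrawing is a risk left open, not a described practice. Re-use would affect about 63% of 15 blocks or 80% of 30 blocks if there were one envelope per pattern, 11% to 36% with a re-used pool of 15 to 60 envelopes that is at least as large as the number of blocks, and 0% with single-use envelopes.

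A reader might go further and conclude that the sequence is known to be unfixed, that researchers can always read the next arm, or that the results will be biased. The documents do not support any of these. Foreknowledge could influence booking or consent and could bias the self-reported outcomes; the size of such bias cannot be calculated from the plan. Single-use envelopes alone would not settle the matter, because each would still hold a whole block.

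**What to change.** In the block randomisation paragraphs of Implementation Design, replace the shared spreadsheet and the block envelopes with the following:

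1. Generate the whole list for 120 patients once, before the first patient, with a recorded seed, and save it as fixed values.
2. Have it held by an existing colleague who neither recruits patients nor delivers GENIE. That person also fills the envelopes.
3. Use sealed, opaque, consecutively numbered, single-use envelopes, each holding one participant's allocation.
4. Open them in number order and only after consent, with the participant ID, date and time logged before opening. No number is drawn in clinic.

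One allocation per envelope is essential, because it removes the whole-block disclosure. With block size four fixed and known, 33.3% of allocations would still be determined by those before them. Varying the block size, without telling those who recruit, would reduce this and could be added when the list is made.

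The cost is a few lines of protocol text and a small amount of a non-recruiting colleague's time. The documents give no figure for that time and do not name such a colleague, so availability is an assumption. Researchers could no longer consult the list, and blocks would no longer match clinic sessions. No extra patients or visits are needed.

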The main aim here is to increase long term health care management options in Solent NHS Trust by building social capacity to support self-management. The GENIE tool will be introduced into the COPD service to improve options for social groups and exercise when leaving a pulmonary rehabilitation group, or when clinically unable to participate in exercise.

- to build social networking awareness and the importance of utilising existing social resources in the professional and voluntary members of the COPD service,
- to use social network mapping techniques and preference elicitation to engage COPD patients in reflecting on their support preferences and needs, help them access further resources and knowledge
- Evaluate the success of the social mapping techniques (GENIE) in the COPD patient population
- Evaluate the cost benefit to both to patients and to the health service of the GENIE in the COPD patient population

Objectives

Primary objectives

Compare and evaluate the health care utilisation and quality of life (burden of disease) in COPD patients using GENIE alongside usual care after leaving the COPD service with those offered only a current practice discharge plan.

Secondary objectives

Compare and evaluate the change in health behaviours, in particular diet and lifestyle in COPD patients using GENIE alongside usual care after leaving the COPD service with those offered only a current practice discharge plan.

Observe and understand the uptake and utilisation of the GENIE recommendations by COPD patients.

Explore social complexities in the COPD population.

Implementation Design

[figure not shown]
This protocol is concerned with the implementation and evaluation of the GENIE tool in the community facilitated by the COPD team and the subsequent evaluation of the GENIE in direct comparison to usual clinical practice.

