Stage 3: This section will then link individuals to prioritised and valued activities and resources (links are to a pre-created database where local organisations and resources have been categorised).

Stage 4: The GENIE Tool then presents options in a user-friendly way, on a Google map with clear details about access, an example below:

Both groups will receive usual care, however one arm will have the addition of the intervention both will be called for a review at:

Three monthly follow up (+/- 1 week)

Six questionnaires will be administered. EQ-5D, health utilisation questionnaire, HEIQ and wellbeing questionnaires (CAT, GAD, PHQ-9), as well as the optional health behaviour questionnaire, so in 30 participants this will be seven, these will be repeated at 3 months post intervention (+/- 2 week). Furthermore, for those in the intervention arm, feedback and reflection discussions will be initiated using the network diagrams. Participants will be asked again for their permission to tape record these discussions to ensure parity and quality assurance between researchers.

Analysis of Outcomes

The study gathers data from the intervention arm and the non-intervention arm at baseline and 3 months post intervention. Results will be compared between the groups at baseline and 3 months post intervention. An economic analysis will be performed using a modified version of the Client Service Receipt Inventory (CSRI) (Beecham and Knapp 1999) Medication, health service use will be measured at baseline, 3 months post implementation and follow up. The modified version has been tailored to capture the needs of the target population (COPD patients). The CSRI has been widely used in previous research studies and has been evidenced as a valid measure of frequency of health service use (Patel 2005). The EQ5D is included to assess health status of patients during the GENIE intervention. Wellbeing score (CAT) and HEIQ and in the optional sub-group health behaviours (dietary intake, appetite, alcohol consumption and smoking habits) will be compared at baseline and 3 months. Furthermore, patient uptake of the social activities is to be recorded on paper using the Genie tool and compared between groups.

Rationale for the service implementation and evaluation design

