Participation in the study will be offered to every patient in pulmonary rehabilitation or maintenance exercise programs in the east of Southampton. Participants must also fulfill the inclusion criteria. Patients already referred into pulmonary rehabilitation groups will be approached and asked if they wish to participate in the study at assessment and at the end of pulmonary rehabilitation in their post PR review appointment. The appointments are offered to patients after completion of the patients PR program, usually after 12 sessions by the clinical team. Therefore, it is envisaged that a minimum of 30 patients per arm will be recruited; these include PR leavers, maintenance reviews referrals. Appointments will be offered in person, via the telephone with confirmation letter or text. The numbers from each of these groups cannot be predicted as it is dependent on clinical opinion, however the aim to have a minimum of 30 participants, with the aim to recruit up to 60 to ensure meaningful analysis.

Inclusion criteria;

- adults between 18 and 95 with a predominant diagnosis of COPD
- Ability to understand spoken English
- Enrolled in PR or maintenance therapy
- Ability and capacity to make their own decision and consent freely

Exclusion Criteria;

- No clear COPD diagnosis
- Inability to consent

The Intervention

This evaluation aims to demonstrate the effectiveness and increase social interactions and community networks in the COPD population in Southampton city.

Rational for GENIE is connecting people to new resources

The aim of using GENIE is to connect people with long-term conditions to local and (in the future) online resources to support them in their everyday lives. Objectives of GENIE:

- Raise awareness of the links and functions that social networks enable (for individuals and local community groups and organisations).
- Use social networks to engage patients in reflecting on their needs and support, support access to further resources and knowledge and introduce practices related to lifestyle, illness management, and behaviour change.
- Strengthen existing individual and community networks and improve patient engagement.

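### The health-behaviour comparison relies on an optional form whose opt-in is not fixed before allocation and whose baseline is placed after randomisation, so it may lose the protection of randomisation

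*Combined protocol and SAP*

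**What the plan says.** The secondary objectives include a between-arm question: "Compare and evaluate the change in health behaviours, in particular diet and lifestyle in COPD patients using GENIE alongside usual care", set against patients given only the current discharge plan.

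The instrument is collected "as well as an optional health behaviour questionnaire, from both the usual care group and the interventional group" (Initial / Baseline data collection) and repeated at 3 months. The three-month follow-up text names six questionnaires and adds this one, "as well as the optional health behaviour questionnaire, so in 30 participants this will be seven". Analysis of Outcomes says only that "in the optional sub-group health behaviours (dietary intake, appetite, alcohol consumption and smoking habits) will be compared at baseline and 3 months".

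On sequence, the paragraphs on selection and patient information describe consent and randomisation, then delivery of care by arm, and then state: "Baseline questionnaires will also be administered at this visit". The Table of Events has a first column for consent and randomisation and a second for pre-intervention data collection; the optional form sits in the second. Randomisation is in blocks of four, with one envelope holding the allocation pattern for a whole clinic.

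No blinding of participants or researchers is described. The Analysis Plan announces five sections and lists four, a) to d); none covers health behaviours.

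**The concern.** The objective asks about an effect of allocation, so it needs two groups that differ only by chance at the start. A voluntary form weakens this if the decision to complete it is taken when the arm is already known. Someone just offered help with community activities may be more, or less, willing to answer questions on diet, alcohol and smoking than someone who was not.

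Baseline answers raise a related problem. The objective concerns change, so every result is measured from the baseline form. If that form is filled in after the arm is known, the starting point itself can be coloured by allocation, even among people who agreed to take part beforehand.

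At stake is whether a difference in diet or lifestyle could be credited to GENIE. The primary objectives do not depend on this form.

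**Working it through.** **Counts in the plan.** Six named questionnaires (EQ-5D, health utilisation, HEIQ, CAT, GAD, PHQ-9) plus the optional one make seven, as stated. The trial size, 2 × 60 = 120, also agrees with the text. No alpha, power, effect size, SD or dropout is given for the trial or for the optional form, so there is no power calculation to reproduce.

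**What 30 can mean.** The block-randomisation text uses 30 as a per-group minimum: "recruitment needs to reach at least 30 patients, in each group, however the maximum could be 60 in each group, 120 patients in total". The Population section also uses it without reference to an arm: "the aim to have a minimum of 30 participants, with the aim to recruit up to 60 to ensure meaningful analysis".
- As a total, 30 is 30/120 = 25% to 30/60 = 50% of those randomised.
- As 30 per arm, it is 60/120 = 50% to 60/60 = 100%. At the minimum size that is everyone, which sits badly with the description of an optional sub-group. A total is the more natural reading, but it is not stated.

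**Precision (assumed: two-sided 5%, 80% power, equal split, no dropout).** In SD units of the outcome compared, the normal approximation is (1.960 + 0.842) × √(2/n per arm); the t-test value is slightly larger.

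| n per arm | Situation | Normal | t-test | t-test power for 0.5 SD |
|---|---|---|---|---|
| 15 | 30 is a total | 2.802 × √(2/15) = 1.02 | 1.06 | 26% |
| 30 | 30 is per arm, or all of 60 complete | 2.802 × √(2/30) = 0.72 | 0.74 | 48% |
| 60 | all of 120 complete | 2.802 × √(2/60) = 0.51 | 0.52 | 78% |

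The trial as a whole is balanced by design (the envelope scheme "ensures 50/50 grouping of participants"), but that does not carry over to a voluntary subset. A 10/20 split of 30 people gives 2.802 × √(1/10 + 1/20) = 1.09 SD by the normal approximation.

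**Sequence.** Set side by side, the two places that give an order agree: consent, randomisation, then baseline questionnaires, all before or around delivery of the intervention. Neither says when the optional form is agreed to. Two routes for allocation to affect the data follow:
1. Who supplies data. This route is open if opt-in follows disclosure of the arm. It is closed if opt-in is recorded beforehand.
2. What is reported at baseline. This route stays open under the stated sequence whenever opt-in was agreed.

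**Illustration of route 1, for the level of a behaviour only.** Suppose those highest on a standard normal willingness trait opt in: 50% in one arm and 30% in the other. Mean willingness among those who opt in is 0.798 and 1.159, a difference of 0.361. If willingness correlates 0.3 to 0.5 with the level of the behaviour, the arms differ by 0.361 × 0.3 = 0.11 to 0.361 × 0.5 = 0.18 SD with no true effect. In this model equal opt-in rates give zero. All these inputs are assumed, and the figure does not transfer to change: a stable difference in level is present at both visits and largely cancels.

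**The case against.** The strongest answer is that the documents never say opt-in happens after allocation. They order data collection, not the decision to take part. The consent form is a separate document that was not available here, and an optional component may well be agreed on it before any envelope is opened. In that case the comparison within the opted-in set stays randomised, only smaller and less general. This stands. A reader might infer that the health-behaviour result is simply not a randomised comparison; the documents do not support that.

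Three further points also stand:
- A reader might take the analysis to have 15 per arm. The text does not say whether 30 is a total or per arm, and on the per-arm reading the detectable difference at the minimum trial size is no worse than if every participant completed the form.
- A reader might suppose that only 30 people will be offered the form. The baseline section and the Table of Events list it for both arms with no cap, so 30 may be the expected uptake of an open offer. Self-selection is a fair reading of an optional form, but no selection rule is given.
- Bias in change needs willingness to be related to change itself, for which the documents offer no value.

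The objection does not answer the stated order of baseline questionnaires. A tick at consent would settle who is in the set, but the baseline form would still follow randomisation with no blinding described.

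**Conclusion.** The concern holds in a limited form. As written, the plan allows known allocation to affect who completes the health-behaviour form and what they report at baseline, so this comparison may lose the protection of randomisation. Whether it does depends on facts not in the documents. There is no selection bias if opt-in is fixed before allocation, or if it does not differ by arm in rate or in kind of person.

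No size can be put on the bias in change. Precision is low on either reading of the 30: about 1.06 SD detectable with 15 per arm and 0.74 SD with 30 per arm, on the assumed 5% two-sided test, 80% power, equal split and no dropout. This affects one secondary objective, and the correction is nearly free; it is an improvement worth making rather than a serious flaw.

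**What to change.** - Record opt-in to the health-behaviour form at consent, and complete its baseline version before the envelope for that clinic is opened. Amend the selection text and the Table of Events to show this order.
- Define the analysis set as those who opted in at that point, and compare arms within it.
- Report opt-in, and completion at 3 months, by arm. The reordering does not prevent differential loss after baseline, so the reader needs to see it.
- Add the comparison to the Analysis Plan, labelled exploratory, with a 95% interval.
- State whether 30 is a total or per arm, and whether it is a cap or expected uptake.

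The form stays voluntary. The cost is one tick box and a change in the order of forms within the same visit. Because one envelope covers a clinic of four, the order has to be kept for everyone in that clinic. The protocol does not say whether the four attend together; if they do not, the clinic timetable needs a small adjustment.
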